## Study Duration

The study will commence as soon as we receive IRB approval and OSP clearance. The project enrollment period will last approximately three years with one year to clean the data and analyze results.

## Study Outcome Measures (Endpoints)

- Maternal demographics (listed under the data collection section of the protocol)
- Infant measures (listed under the data collection section of the protocol)

Current Version Date:	9/10/2020	IRBNet #: 1170748
Previous Version Date:		Page 14 of 25

- Incidence of death or BPD measured at 36 weeks post menstrual age (yes or no)
  - BPD will be defined as need for supplemental oxygen for at least 28 days. Severity of BPD will be determined at 36 weeks postmenstrual age. Infants with no need for supplemental oxygen will be classified as mild BPD. Continued requirement for supplemental oxygen (<0.3 FiO2) will be considered moderate BPD. Infants requiring >0.3 FiO2 and or positive pressure respiratory support will be diagnosed with severe BPD. The need for continuing oxygen therapy will be determined by a room air challenge. We will prospectively collect data that will allow us to define BPD as recommended by the 2018 NICHD report
- Pulmonary arterial pressure based on serial echocardiograms)
- Oxygen saturation level (average for each 24-hour period after enrollment)
- Arterial pressure and oxygen saturation will be measured up to 2-weeks or until the treatment is discontinued, whichever is shorter.

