### **Data Collection:**

Demographic and clinical data will be prospectively collected from maternal and neonatal charts along with data from serial echocardiograms. Following variables will be included in the database

- **Maternal Data:** Age, ethnicity, educational level, smoking, alcohol or illicit use of drugs, medication history, any medical or surgical problem, antenatal screening lab results (GBS, HIV, HBs Ag, RPR) maternal UTI, chorioamnionitis, rupture of membrane, vaginal bleeding or discharge, antenatal antibiotics, steroids, indomethacin or magnesium.
- **Neonatal Data: BPD our primary outcome is determined based on the need for positive pressure ventilation or supplemental oxygen after room air challenge test**  
Gestation, Gender, mode of delivery, Apgar scores, IUGR, Birth Weight, Surfactant, Ventilation, pulmonary hypertension (early, intermittent or late), use of supplemental oxygen, culture proven infections, blood transfusions, Cardiotropic medication, bicarb infusion, saline boluses, use of indomethacin, PDA treatment/ ligation, use of diuretics, use of postnatal steroids, IVH, PVL, Post IVH hydrocephalus, NEC, ROP, ROP requiring treatment, VP shunt, Tracheostomy, Gastrostomy tube, home oxygen, home ventilation, length of hospital stay and death.

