## Sample Size Determination

Sample size was calculated based on our pilot study showing that the incidence of death or BPD among extremely preterm infants with early pulmonary hypertension was 80%. Assuming a 30% relative decrease of the incidence we came up with a sample size of 34 infants in each arm with 80% power and alpha of 0.05.

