## Statistical Analysis Plan

### Primary Objective Analysis

Data will be analyzed to define the demographic and clinical characteristics of the two study cohorts (iNO and placebo) and the infants without early PH (not enrolled for treatment, please see Fig. 1). Chi square test for categorical variables and student's t test or non-parametric equivalent test for continuous variables will be used. Relative Risk (with 95% CI) for death or BPD will be calculated for the placebo and iNO treatment groups. The outcomes of infants without early PH will also be compared with the two study cohorts (iNO and placebo). Logistic regression will be performed to adjust for significant covariates if needed (unlikely because of randomization and stratification). Similarly, treatment and placebo groups will be compared to determine the short-term benefits of iNO treatment for PH in preterm infants.

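### The BPD half of the primary endpoint has two conflicting rules, and the plan does not say whether mild BPD counts as an event

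*Combined protocol and SAP*

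**What the plan says.** Study Outcome Measures (Endpoints) lists a binary composite: "Incidence of death or BPD measured at 36 weeks post menstrual age (yes or no"). Beneath it, the same section says "BPD will be defined as need for supplemental oxygen for at least 28 days". It then gives the 36-week assessment a grading role: "Severity of BPD will be determined at 36 weeks postmenstrual age", and "Infants with no need for supplemental oxygen will be classified as mild BPD". Moderate and severe grades follow from oxygen concentration and positive pressure support at that time. The room air challenge is used there to establish continuing oxygen need. A third definition appears without a role in the analysis: "We will prospectively collect data that will allow us to define BPD as recommended by the 2018 NICHD report".

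The Data Collection section, under Neonatal Data, says: "BPD our primary outcome is determined based on the need for positive pressure ventilation or supplemental oxygen after room air challenge test". It has no 28-day criterion, no mild category and no time point.

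Sample Size Determination takes from the pilot study that the "incidence of death or BPD among extremely preterm infants with early pulmonary hypertension was 80" per cent. Primary Objective Analysis says "Relative Risk (with 95% CI) for death or BPD will be calculated for the placebo and iNO treatment groups". Neither says which BPD rule is meant.

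**The concern.** The two statements sort the same infants differently, and this is the trial's primary endpoint. The number of events in each arm, the relative risk and its interval, and the meaning of the 80% planning rate all depend on which rule is used. If that is not fixed in writing, it can be settled once the results under both rules are visible.

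The rules also ask different questions. If any grade of BPD counts, an effect of iNO that moves infants from moderate or severe to mild disease leaves the primary endpoint unchanged. If only need for support at 36 weeks counts, that effect is captured. Either endpoint can be defended, but the plan has to say which one it is testing.

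**Working it through.** **Step 1: apply each rule to the infants on whom they could differ.** The Data Collection rule has no time point, so 36 weeks is borrowed here from the endpoint line.

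| Infant | Study Outcome Measures rule | Data Collection rule |
|---|---|---|
| At least 28 days of oxygen, no support at 36 weeks | BPD (mild): event | Passes the challenge: not an event |
| At least 28 days of oxygen, needs oxygen or positive pressure at 36 weeks | BPD (moderate or severe): event | Event |
| Under 28 days of oxygen, on positive pressure at 36 weeks | Not BPD: not an event | Event |
| Under 28 days of oxygen, no support at 36 weeks | Not an event | Not an event |

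Rows 1 and 3 disagree. Row 1 is the mild-BPD group. The documents give no frequency for row 3, so it carries little weight here.

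**Step 2: look for a rule of precedence.** The endpoint line fits either reading: any-grade BPD ascertained by 36 weeks, or support needed at 36 weeks. The sample size and analysis sections use the composite's name only. No section ranks one definition over the other.

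**Step 3: illustrate the effect on the primary result.** The documents give 34 per arm and a relative risk with 95% CI. All event and mild-BPD counts below are hypothetical, except that 19 and 27 of 34 approximate the planned 56% and 80% (0.80 × 0.70 = 0.56).

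For a events on iNO and b on placebo, RR = a/b with equal arms, and the CI is exp[ln RR ± 1.96 × √(1/a − 1/34 + 1/b − 1/34)]. P-values are from the uncorrected chi-square test.

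| Scenario | Rule | iNO vs placebo events | RR (95% CI) | p |
|---|---|---|---|---|
| 1 | Any grade | 24 vs 27 | 0.89 (0.67–1.17) | 0.40 |
| 1 | Support at 36 weeks (10 and 4 mild removed) | 14 vs 23 | 0.61 (0.38–0.97) | 0.028 |
| 2 | Any grade | 19 vs 27 | 0.70 (0.50–0.99) | 0.038 |
| 2 | Support at 36 weeks (3 and 7 mild removed) | 16 vs 20 | 0.80 (0.51–1.26) | 0.33 |

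Worked example for 14 vs 23: RR = 14/23 = 0.609; SE = √(1/14 − 1/34 + 1/23 − 1/34) = 0.237; CI = exp(ln 0.609 ± 1.96 × 0.237) = 0.38 to 0.97.

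**Step 4: effect on power if the 80% was an any-grade rate.** That premise is an assumption, as are the lower control rates. The formula is power = Φ{[|p1 − p2|√n − 1.96√(2p̄(1 − p̄))] / √(p1(1 − p1) + p2(1 − p2))}, with n = 34, two-sided 0.05 and p̄ the mean of p1 and p2. The plan does not state sidedness.

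The plan's own rates, 80% vs 56%, give 57% and not the stated 80%. That shortfall is a separate sample-size matter and is shown only as the reference.

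| 36-week control rate (assumed) | 30% relative decrease kept | 24-point absolute decrease kept |
|---|---|---|
| 70% | vs 49%: 42% | vs 46%: 52% |
| 60% | vs 42%: 31% | vs 36%: 51% |
| 50% | vs 35%: 24% | vs 26%: 53% |

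The loss from the 57% reference is therefore large if the relative effect is held fixed and small (4 to 6 points) if the absolute effect is held fixed.

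**The case against.** The best defence is that the endpoints section governs. It contains the explicit definition, directly under the endpoint line, and on its plain words mild BPD is BPD. Later sections need not repeat it. The Data Collection sentence heads a list of variables, gives no time point, and may be shorthand for the assessment method, since the endpoints section also uses a room air challenge.

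That reading is possible but does not remove the conflict. In the endpoints section the challenge establishes continuing oxygen need and so separates grades; in Data Collection it decides BPD itself, in the sentence that names BPD as the primary outcome. If shorthand was intended, the plan still has to say so and say that mild cases count.

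A second objection does stand against the illustration. Both significant results are borderline and depend on the test. For 14 vs 23, Fisher's exact and the continuity-corrected p-values are both 0.051; for 19 vs 27 they are 0.068 and 0.070. With those tests neither scenario crosses 0.05. The analysis plan names chi-square without mentioning a correction, and the relative-risk intervals it asks for do exclude 1 in both cases. It is also fair to say that the power loss is small under a fixed absolute effect, and that preferring an endpoint sensitive to severity is a judgement, not an inconsistency.

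**Conclusion.** The concern holds and must be fixed. The plan contains two rules for the BPD component of its primary endpoint, they disagree on infants with mild BPD, and nothing in the documents resolves the disagreement or says which rule produced the 80%. This conclusion rests on the text alone, apart from applying the Data Collection rule at 36 weeks.

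The size of the effect is unknown because no mild-BPD share is given. The hypothetical counts show that the relative-risk conclusion can change in either direction at 34 per arm; they do not show that it will. The power figures hold only if the 80% was an any-grade rate and the 36-week rate is lower.

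**What to change.** Before unblinding, write one primary definition into Data Collection, Study Outcome Measures and Primary Objective Analysis, with its time point and an explicit statement on whether mild BPD is an event. Two versions are consistent with existing text:

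- **Support at 36 weeks:** death by 36 weeks postmenstrual age, or need for supplemental oxygen or positive pressure at 36 weeks after the room air challenge. Mild BPD is not an event. This follows Data Collection combined with the endpoint line.
- **28-day rule:** keep the current definition in Study Outcome Measures, correct Data Collection to match, and state that any grade counts. This is the smaller edit.

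In Sample Size Determination, say which definition the pilot study's 80% used. Adopt that definition, or restate the planning rate and sample size for the one chosen. Report the other definition and the 2018 NICHD grade as secondary outcomes.

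The cost is protocol and SAP wording, since the oxygen, ventilation and room air challenge data are already to be collected. The one real cost arises if the chosen definition is not the one behind the 80%: the planning rate, and possibly the sample size, must then be restated.

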### **Step 1:**

#### **Inclusion Criteria:**

These infants are eligible for echocardiographic screening of early pulmonary hypertension:

1. Extremely preterm infants born at  $23^{0/7}$ - $29^{6/7}$  weeks gestation admitted to our neonatal ICU
2. Positive pressure ventilation at 48-96 hours of age, irrespective of oxygen concentration via ETT or CPAP

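### The plan gives two conflicting BPD rules for the primary endpoint: an infant on positive pressure in 21% oxygen at 36 weeks with under 28 oxygen days is an event under only one

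*Combined protocol and SAP*

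**What the plan says.** The endpoint is listed under Study Outcome Measures (Endpoints) as a yes/no incidence of death or BPD at 36 weeks postmenstrual age. The BPD component is then described in more than one way.

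- **Study Outcome Measures (Endpoints), entry rule:** "BPD will be defined as need for supplemental oxygen for at least 28 days". Positive pressure is not mentioned in this sentence.
- **Same section, severity at 36 weeks:** "Infants with no need for supplemental oxygen will be classified as mild BPD". FiO2 below 0.3 is moderate. For FiO2 above 0.3 the text continues "and or positive pressure respiratory support will be diagnosed with severe BPD". A room air challenge settles whether oxygen is still needed.
- **Same section, a further definition:** "We will prospectively collect data that will allow us to define BPD as recommended by the 2018 NICHD report". No role in the analysis is given to it.
- **Data Collection:** "BPD our primary outcome is determined based on the need for positive pressure ventilation or supplemental oxygen after room air challenge test". This line has no duration condition and states no time point of its own.

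Sample Size Determination takes an 80% rate of death or BPD from the pilot without stating the pilot's BPD definition. Primary Objective Analysis plans a relative risk with 95% CI for death or BPD, also without naming a definition.

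**The concern.** The two rules differ on what makes an infant a case. The endpoint section asks for a duration of oxygen. The data collection section asks for a need for oxygen or for pressure. The rules disagree on an infant who still needs positive pressure at 36 weeks, breathes 21% oxygen, and has not accumulated 28 oxygen days.

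In a trial of 68 randomized infants with a binary primary endpoint, the classification of a single infant can matter. If the rule is still open when the data are seen, the choice between two sentences of the protocol could settle the result. On the oxygen-duration rule, an infant who has not come off respiratory support would also be counted as a treatment success.

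**Working it through.** **Step 1. Apply each rule to the infants on whom they could differ.** The Data Collection rule is applied at 36 weeks, the time given for the endpoint; that line does not state a time itself.

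| Infant at 36 weeks | Oxygen days | Endpoints section | Data Collection section |
|---|---|---|---|
| A: positive pressure, 21% oxygen | under 28 | no BPD | event |
| B: positive pressure, 21% oxygen | 28 or more | event; fits both mild and severe wording | event |
| C: no oxygen, no pressure | 28 or more | event (mild) | not an event |
| D: FiO2 exactly 0.30, no pressure | 28 or more | event; no severity class | event |

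A and C change the yes/no endpoint. B and D change only the grade. A is the subject of this point; C is the same conflict running the other way, and the remedy has to settle it too.

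**Step 2. Inputs for the size.**
- Per arm: 34 (Study Site(s)/Location(s) and Number of Subjects; Sample Size Determination).
- Control rate 80%, relative decrease 30% (Sample Size Determination), so the iNO rate is 0.80 × 0.70 = 56%.
- Illustrative events: 0.80 × 34 = 27.2, taken as 27; 0.56 × 34 = 19.04, taken as 19.
- Number of type A infants: not given. Assumed 0, 1 or 2 per arm.

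The stated 34 per arm is not reproduced from these rates (59 per arm by the two-sided pooled formula at 80% power). That is a separate matter; here 34 serves only as the planned denominator.

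**Step 3. Formulas.** With a placebo events and b iNO events, n = 34:
- pooled rate p̄ = (a + b)/68
- z = [(a − b)/34] / √[p̄(1 − p̄) × 2/34], two-sided p (Pearson chi-square without continuity correction)
- RR = b/a; 95% CI = exp{ln RR ± 1.96 √(1/a − 1/34 + 1/b − 1/34)}
- one infant = 1/34 = 2.9 points

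For 27 versus 19: p̄ = 46/68 = 0.676, z = 0.2353/0.1135 = 2.07, p = 0.038.

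**Step 4. Results, adding type A infants as events.**

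| Added | Placebo vs iNO | p | RR (95% CI) |
|---|---|---|---|
| none | 27 vs 19 | 0.038 | 0.70 (0.50–0.99) |
| 1 to iNO | 27 vs 20 | 0.066 | 0.74 (0.53–1.03) |
| 2 to iNO | 27 vs 21 | 0.110 | 0.78 (0.57–1.07) |
| 1 to each arm | 28 vs 20 | 0.033 | 0.71 (0.52–0.98) |
| 2 to each arm | 29 vs 21 | 0.028 | 0.72 (0.54–0.98) |
| 1 to placebo | 28 vs 19 | 0.018 | 0.68 (0.48–0.95) |

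One extra event on the iNO side takes the interval across 1. Equal additions barely change the result, and an addition to placebo alone strengthens it.

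The plan does not say whether the chi-square is corrected. Fisher's exact test gives p = 0.068 for 27 versus 19 and 0.034 for 28 versus 19, so on that test too one infant can move the result across 0.05.

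**The case against.** The defence is that the endpoint section is the proper home of the definition and is clear for infant A. It defines BPD first and grades it afterwards, so an infant who fails the 28-day condition is never graded. The competing sentence is one line in a list of variables. Such an infant must also be on pressure some 6 to 13 weeks after birth without ever reaching 28 oxygen days, and the documents do not show that any exist.

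Much of this stands, and it rules out several stronger readings a reader might infer:

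- **That the 28-day rule misses every infant on pressure in 21% oxygen.** It misses only those with fewer than 28 oxygen days; infant B is an event.
- **That the endpoint section contradicts itself by calling infant A severe.** The words "positive pressure respiratory support will be diagnosed with severe BPD" grade infants who already have BPD.
- **That the mild/severe overlap or the gap at FiO2 0.30 moves the primary endpoint.** Both affect grade only, and no severity analysis is specified.
- **That eligibility guarantees such infants.** The criterion "Positive pressure ventilation at 48-96 hours of age, irrespective of oxygen concentration via ETT or CPAP" describes support at entry, not at 36 weeks.
- **That the rule favours iNO.** That would require iNO to shorten oxygen exposure while pressure support continues. The secondary objective expects better oxygenation, but nothing in the documents establishes that shift.

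The objection does not dispose of the conflict between sections. The Data Collection line explicitly calls BPD the primary outcome and states how it is determined, and no text ranks one section above the other.

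**Conclusion.** The concern holds as a conflict between two sections over the BPD component of the primary endpoint. An infant on positive pressure in 21% oxygen at 36 weeks with under 28 oxygen days is a non-event under the endpoint section and an event under Data Collection. Neither Sample Size Determination nor Primary Objective Analysis resolves it.

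The size per infant is certain: 2.9 points of an arm's rate. The total effect is not known, because the number of such infants is not given and may be zero. At counts near the design rates, one infant can carry the result across the 0.05 line or make it firmer, depending on the arm. The p-values rest on illustrative counts and an uncorrected chi-square. No direction of bias can be claimed.

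**What to change.** Before unblinding, write one BPD rule for the primary endpoint and use it identically in Data Collection, Study Outcome Measures (Endpoints) and Primary Objective Analysis. It should:

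1. Count any infant on positive pressure at 36 weeks postmenstrual age as an event, at any FiO2 and whatever the oxygen-day count, consistent with Data Collection.
2. Say explicitly whether 28 oxygen days with no support at 36 weeks is an event. Without this, the two sections would still disagree.
3. Give the 2018 NICHD definition a stated role, for example a sensitivity analysis.

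Sample Size Determination should state which definition produced the pilot's 80%.

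As a tidy-up that affects grading only, make mild exclude infants on positive pressure and assign FiO2 of exactly 0.30 to one class.

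The cost is a few sentences. Ventilation and supplemental oxygen use are already on the data collection list. The downside is that the event rate may differ slightly from 80% if the pilot used another definition.

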### **Secondary Objective/Aim/Goal/Hypothesis:**

Secondary objective is to show that iNO treatment of extremely preterm infants with early PH will decrease the pulmonary artery pressure and improve the oxygenation within 72 hours of intervention. The change in pulmonary artery pressure and oxygenation from

Current Version Date:	9/10/2020	IRBNet #: 1170748
Previous Version Date:		Page 5 of 25

initiation of treatment () to 3 days later (approximately 72 hours later) will be compared for the two treatment arms.

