## Study Visits:

[figure not shown]
Infants with early pulmonary hypertension will be randomized to the treatment group or the placebo group (see randomization plan). iNO or placebo treatment will start at 20 ppm. Treatment will continue for 2 weeks or until resolution of pulmonary hypertension, whichever comes first.

Current Version	9/10/2020	IRBNet #: 1170748
Date:		
Previous Version		Page 12 of 25
Date:		

To ensure the safety and evaluate the clinical response to iNO treatment, we will perform serial echocardiograms as shown in figure 2.

Figure 2

Time Line for Serial Echocardiography

\*PMA: Post Menstrual Age  
+ PH: Pulmonary Hypertension

Since the data of SpO2 & FiO2 are available in all infants, their ratios (SF ratio) will be calculated as markers of improved oxygenation. SF ratio has the advantage of avoiding invasive arterial blood sampling in situation when umbilical arterial line is unavailable. It is a reliable noninvasive surrogate for PaO2: FiO2 ratio to identify children with severe lung disease. Respiratory Severity Score (RSS= FiO2 X Mean airway pressure (MAP)) will be monitored for infants on mechanical ventilation since the data of mean airway pressure will be available. Significant response to iNO treatment will be defined as 20% improvement in SF ratio or resolution of pulmonary hypertension (assessed by echo) within 72 hours. Serial echocardiograms will be performed every 24-48 ± 12 hours until 14 days of life irrespective of the length of treatment.

Current Version 9/10/2020  
Date:

IRBNet #: 1170748

Previous Version  
Date:

Page 13 of 25

If PH is resolved during the 2-week treatment window or after the completion of the 2-week treatment protocol, we will start weaning the iNO dose by decreasing to 15 ppm. Weaning will continue to 10, 5, 4, 3, 2 and 1 ppm every 4 hours. During the weaning process if SF ratio decreased by 20%, iNO /Placebo dose will be increased to the minimum dose where  $\text{FiO}_2$  and  $\text{PaO}_2$  were stable. Weaning can be resumed after 12 hours following the above guidelines. The iNO weaning process described above is the current standard of care in our NICU for infants with PH. If pulmonary hypertension recurs in the first 2 weeks of life after stopping the treatment, iNO/Placebo treatment will be resumed based upon the randomization at the time of enrollment.

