About 1/3 of term and near-term infants with pulmonary hypertension may not respond to iNO. We will evaluate the effectiveness of iNO treatment by recording changes in serial echocardiogram and in mean airway pressure (MAP),  $\text{FiO}_2$ ,  $\text{SpO}_2/\text{FiO}_2$  ratio, and oxygenation index (OI) before and at  $24 \pm 6$ ,  $48 \pm 6$ , and  $72 \pm 12$  hours after beginning therapy. Non-responders will be defined as no improvement in pulmonary artery pressure or cardiac function on three serial echocardiograms and lack of 10% improvements from baseline for MAP,  $\text{FiO}_2$ ,  $\text{SpO}_2/\text{FiO}_2$  ratio and OI at  $72 \pm 12$  hours after starting treatment. Once an infant is identified as a non-responder, we will start weaning treatment (iNO or placebo) as described in our iNO weaning plan given below. It is important because even in "non-responders," one can still see significant rebound pulmonary hypertension with iNO discontinuation. If pulmonary hypertension is noted on subsequent echocardiograms, study intervention will not be resumed for non-responders. However, there is no restriction on clinical team to start iNO if needed based on clinical criteria.

During the course of hospitalization, all infants will receive standard of care and will be monitored as per NICU monitoring. Per AdventHealth NICU standardized guidelines, target oxygen saturations for  $\leq 32$  weeks PMA is 86-92%. We will follow these guidelines while the subject is receiving supplemental oxygen.

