### Secondary Objective Analysis

We will analyze the change in pulmonary arterial pressure by serial echo within 72 hours of initiation of iNO. We will also compare the pulse oximeter to inspired oxygen ratio.

Current Version	9/10/2020	IRBNet #: 1170748
Date:		
Previous Version		Page 16 of 25
Date:		

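### The endpoint list measures oxygenation by 24-hour mean SpO2 until treatment stops: this is largely insensitive under the saturation target, and matches neither the SpO2/FiO2 analysis nor the 72-hour objective

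*Combined protocol and SAP*

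**What the plan says.** Four parts of the combined protocol and SAP bear on the oxygenation objective.

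- **Secondary Objective.** Treatment "will decrease the pulmonary artery pressure and improve the oxygenation within 72 hours of intervention". The change from the start of treatment to about 72 hours is to be compared between the arms. No oxygenation variable is named.
- **Study Outcome Measures (Endpoints).** The only oxygenation measure named is "Oxygen saturation level (average for each 24-hour period after enrollment". The last bullet sets its window: "Arterial pressure and oxygen saturation will be measured up to 2-weeks or until the treatment is discontinued, whichever is shorter".
- **Study Visits.** SpO2 and FiO2 are available in all infants, and "their ratios (SF ratio) will be calculated as markers of improved oxygenation". Response includes a 20% improvement in this ratio within 72 hours. The non-responder rule uses 10% for mean airway pressure, FiO2, the ratio and the oxygenation index. These are recorded before treatment and at 24 ± 6, 48 ± 6 and 72 ± 12 hours. The same section gives the saturation target for infants up to 32 "weeks PMA is 86-92%. We will follow these guidelines while the subject is receiving supplemental oxygen". It sets no arm-specific rule: "all infants will receive standard of care and will be monitored as per NICU monitoring".
- **Secondary Objective Analysis.** "We will also compare the pulse oximeter to inspired oxygen ratio". No time point or baseline handling is given for the ratio.

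**The concern.** Staff working to a saturation target respond to better gas exchange by turning the oxygen down. The benefit then appears in FiO2, while SpO2 stays near where it was. The endpoint list names SpO2 alone, so on its own it records the quantity being controlled and leaves out the one that moves.

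The list also disagrees with the rest of the plan on variable (SpO2 against SpO2/FiO2), summary (24-hour means against scheduled time points) and window (until treatment stops against about 72 hours). A report that follows the list could show little difference in oxygenation when the ratio shows one. The list's window can also close before 72 hours in the infants whose pulmonary hypertension resolves first. If treatment affects how soon it resolves, that loss would differ between the arms.

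**Working it through.** The plan states no effect size, standard deviation or power for oxygenation, so there is no figure of its own to reproduce.

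**1. Does the target cover the 72-hour comparison?** The oldest eligible infant is born at 29 6/7 weeks (Step 1 inclusion criteria). Take treatment as starting at 96 hours, the end of the randomisation window.

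- At 72 hours of treatment: 29 6/7 weeks + 4 days + 3 days = 30 6/7 weeks.
- After 14 days of treatment: 29 6/7 weeks + 4 days + 14 days = 32 3/7 weeks.

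Every infant is therefore within the 32-week limit at 72 hours. Only the oldest could pass it late in a 2-week course.

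**2. How far can SpO2 move inside the band?**

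- Bottom to top: 92/86 - 1 = 7.0%.
- Middle to top: 92/89 - 1 = 3.4%.

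Both are below the protocol's 10% and 20% thresholds. Since the ratio is SpO2 divided by FiO2, an infant staying within the band can meet those thresholds only if FiO2 falls:

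| Rise in ratio | SpO2 unchanged | SpO2 rises from 86% to 92% |
|---|---|---|
| 20% | FiO2 × 1/1.20 = 0.833 (fall of 16.7%) | FiO2 × 1.0698/1.20 = 0.891 (fall of 10.9%) |
| 10% | FiO2 × 1/1.10 = 0.909 (fall of 9.1%) | FiO2 × 1.0698/1.10 = 0.973 (fall of 2.7%) |

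**3. Illustration (assumed values, not document figures).** At SpO2 90%, let FiO2 fall from 0.40 to 0.30. The ratio goes from 90/0.40 = 225 to 90/0.30 = 300, a rise of 300/225 - 1 = 33%. Mean SpO2 changes by 0.

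**4. When can listed SpO2 collection end?** Study Visits starts weaning when pulmonary hypertension resolves. The levels are 15, 10, 5, 4, 3, 2 and 1 ppm, stepped every 4 hours. Taking 4 hours at each level, 7 × 4 = 28 hours. If resolution is seen on a 24-hour echocardiogram and weaning proceeds without interruption, treatment ends at 24 + 28 = 52 hours. The 72-hour assessment opens at 72 - 12 = 60 hours. Under the last bullet of the endpoint list, such an infant has no SpO2 value in that window.

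**The case against.** The strongest reply is that the plan has already chosen the right measure. The only oxygenation comparison named in Secondary Objective Analysis is the SpO2/FiO2 ratio, and no between-arm test of mean SpO2 is specified. Study Visits provides for FiO2 and the ratio at 24, 48 and 72 hours, without making this conditional on continuing treatment. The endpoint list begins with maternal demographics and infant measures, so it reads partly as a list of collected variables, and SpO2 is the numerator of the ratio.

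Much of this stands, and it limits the point. Three stronger readings are tempting, and the documents do not support them:

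- **Mean SpO2 cannot show improvement.** The target applies only on supplemental oxygen, entry is irrespective of oxygen concentration, and nothing says observed saturations stay inside the band. These exceptions do not make SpO2 a good measure: it can also rise simply because an infant reaches room air and is no longer held to the target.
- **The trial will report no effect on oxygenation.** That would require a test of mean SpO2, which the plan does not contain.
- **FiO2 will be missing.** It is absent from the endpoint list, and the data collection list that it refers to has only use of supplemental oxygen, but Study Visits schedules it.

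Nor can anything be said about detectability from the documents, which give no standard deviations. A simulation that assumes the same SpO2 distribution in both arms would reject at about the 5% level by construction, so it would prove nothing.

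What remains is that the endpoint list differs from the other sections in variable and window, that its stopping rule for collection conflicts with a 72-hour comparison, and that the analysis section fixes neither the time point nor the use of baseline.

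**Conclusion.** The point holds as a matter of alignment and sensitivity for a secondary objective. The listed endpoint is largely insensitive to improved oxygenation while infants are on supplemental oxygen under the target. It also differs from the ratio used elsewhere and from the 72-hour objective, and its collection can stop at about 52 hours, before the 60-hour opening of the 72-hour assessment.

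On size, the band allows at most a 7.0% relative change in SpO2, against the protocol's 10% and 20% thresholds for the ratio. This rests on saturations staying within target and on the target being met mainly by adjusting FiO2, which the protocol implies but does not spell out. The 52-hour figure assumes resolution at a 24-hour echocardiogram, 4 hours at each weaning level and no interruption. How many infants would follow that course is not known from the documents.

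The primary endpoint, death or BPD, is unaffected.

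**What to change.** 1. In Study Outcome Measures, name the SpO2/FiO2 ratio at 72 ± 12 hours after the start of treatment as the oxygenation endpoint, with SpO2 and FiO2 taken at the same Study Visits time points.
2. Amend the last bullet of that section so that these values are collected in all randomised infants whether or not treatment has stopped.
3. In Secondary Objective Analysis, compare the arms on the 72-hour ratio adjusted for the baseline ratio. This may gain precision; the documents give no baseline-to-72-hour correlation, so no amount is claimed.
4. Keep 24-hour mean SpO2 as a descriptive measure only.

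The cost is two edited bullets and one sentence in the analysis section. SpO2 and FiO2 are already available in all infants, and the baseline and 72-hour assessments are already scheduled. The only practical change is to make clear that recording continues to 72 hours after treatment has ended. No oxygen target, dose or weaning rule changes.
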